This will be a prospective randomized control trial with a total of 142 patients. Patients who undergo laparoscopic or open colorectal resection, small bowel resection, or ileostomy reversal with small bowel resection that subsequently develop postoperative ileus will be eligible for enrollment. If they meet inclusion/exclusion criteria, they will be randomized at the time of diagnosis of postoperative ileus to receive Entereg as rescue therapy or to receive conservative standard care.

Patients randomized to the Entereg group will be given 12mg of Entereg two times daily from the time of randomization until the return of bowel function or 5 days. Both groups will be treated with conservative standard care, including bowel rest, reduction in oral diet, and placement of nasogastric tube as clinically indicated.

All patients will follow a standard ERAS pathway after surgery, with early feeding and ambulation, along with opioid minimizing measures as is our standard postoperative protocol.

Primary outcome will be hospital length of stay.

Secondary outcomes will include time to return of bowel function, 30-day morbidity/mortality, complications, reoperation and readmission.

Total number of patients: 142

Patients in each study group: 71

Inclusion criteria

1. Subjects who have benign or malignant colonic or rectal disease that have undergone laparoscopic or open colorectal resection, small bowel resection or ileostomy reversal with small bowel resection and subsequently developed postoperative ileus, defined as:
 - a. Return to NPO status after initial diet attempts, or
 - b. Placement of nasogastric tube
2. Subjects who are 18 years of age and older
3. Subjects of either gender
4. Subjects who are willing and able to adhere to protocol requirements, agree to participate in the study program and provide written and informed consent.

Exclusion criteria

1. Subjects who received Entereg preoperatively.
2. Subjects that have taken therapeutic doses of opioids for more than 7 days immediately prior to surgery.
3. Subjects with severe hepatic impairment.
4. Subjects with end-stage renal disease.
5. Subjects who are pregnant.

6. Subjects who were diagnosed with a complete small bowel obstruction preoperatively.
7. Subjects with a medical condition that may interfere with the use of the study medication Entereg.

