Randomization will take place following enrollment and consent. A numbered, sealed envelope, corresponding to the patients' assigned study number, will be opened by *the study coordinator* indicating to which study group the patient is randomized. The study coordinator will notify the pharmacy which study group the patient has been randomized to. Randomization will be stratified to open or laparoscopic surgery, location of surgery (right/left), stoma reversal and presence or absence of stoma. *This will be kept in a locked key to be revealed at the end of the study.*

Enhanced Recovery After Surgery Pathway

All patients will be managed via standardized accelerated postoperative recovery guidelines, which are currently in use by the division of colorectal surgery at UHCMC. This includes patient-controlled analgesia pump, oral analgesia and diet on the first postoperative day, early postoperative ambulation, and defined discharge criteria.

Study Methods

At the time of diagnosis of postoperative ileus and after enrollment and randomization, all patients will be returned to NPO status. Nasogastric tubes (NGT) may be placed for gastric decompression at the discretion of the surgical team if clinically indicated. In the event that an NGT is placed, medications will be given orally or via the NGT, which will be clamped for 30 minutes after administration. Patients will continue on standard ERAS pathways with the exception of reduction of diet. Antiemetics will be given as clinically indicated; however, no prokinetic or promotility agents will be given as scheduled dosages.

Patients randomized to the study group will be given 12mg of Entereg orally twice a day, from the time of diagnosis of postoperative ileus to the time of return of bowel function and tolerating solid food without vomiting or experiencing significant nausea within 4 h following the meal, or without having to revert to enteral fluids only or for 5 days.

Patients randomized to the control group receive standard postoperative care.

The patient and surgical team will be able to know which arm of the study the patient is in based on documentation in the medical record of the administration of Entereg.

Patients in both groups will remain NPO until the return of bowel function, defined as passage of stool, decrease in nasogastric tube output. At this point, the nasogastric tube will be removed and a trial of oral diet will be attempted per surgeon's discretion.

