Standard discharge criteria will be applied to all patients, including:

- Passage of stool
- Ability to tolerate solid food and to drink comfortably
- Adequate oral analgesia
- Patient's willingness to be discharged.

Data to be collected

The medical/surgical information below will be collected as part of this research study and is all information already available as part of the patients medical chart.

- Patient name, medical record number
- Past Medical History

- Past Surgical history
- Preoperative Medications (including steroids, anticoagulation, opioid use)
- Pre-operative Diagnosis
- Patient Demographics (age, gender, BMI, ASA score)
- Procedure performed
- Time of surgery
- Wound classification
- Estimated blood loss
- Intraoperative transfusion
- Intraoperative IV fluids given
- Conversion from laparoscopic to open procedure
- Stoma creation
- Time/day surgery to ileus
- Time from surgery to medication given
- Time from ileus diagnosis to medication given
- Was there return of bowel function (flatus or stool, solid or liquid, stoma output) prior to ileus
- Intra-abdominal infection/anastomotic leak
- Time/day of return of bowel function post ileus (flatus and stool- solid or liquid, and stoma function)
- Time/day of ability to tolerate oral diet (liquid and solid food)
- Nasogastric tube placement and daily output
- Duration of nasogastric tube
- Use and type of anti-emetics given
- Total number of Entereg doses given
- Post operative complications including reoperation
- Length of stay in hospital, defined as time from surgery to discharge
- 30-day readmissions

The above collected data will be put into a REDCap (Research Electronic Data Capture) database which is a secure web application for managing online surveys and databases. It allows the safe and secure storage of research data including storage of PHI HIPAA identifier fields.

Study Completion

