Completion of participation in the study will be 30 days after the date of surgery. Any readmission up to 30 days post-operatively to the hospital as a direct result of their surgery will be followed. The patients will follow-up with the surgeon in the office in approximately 3-6 weeks, which is considered standard of care for all patients undergoing colorectal surgery and is not considered part of the research study. Any patient for whom follow-up documentation is missing or incomplete shall be contacted via telephone. The purpose of the call will be to simply determine return to function and outcome. Only a co-investigator shall contact the subject and will identify themselves at the beginning of the call. Any subject can reserve the right not to participate in the phone call interview; they would remain in the study.

Patient Withdrawal

A subject has the right to withdraw from the study at any time for any reason without prejudice to their future medical care by the physician or the institution. The investigator and principal site also have the right to withdraw subjects from the study for the reasons listed below. Should a subject (or subject's legally authorized guardian/representative) decide to withdraw or be withdrawn, reasonable efforts will be made to complete and report the observations as thoroughly as possible.

Subjects may be removed from the study, if any one or more of the following events occur:

- Serious Adverse Event
- Noncompliance
- Lost to follow-up
- Investigator/Principal site recommendation

- Withdrawal of consent
- Protocol Violation
- Intercurrent illness
- The investigator considers it in the patient's best interest to do so

This study is estimated to take 24 months for completion.

Statistical Plan

After recruitment of 71 patients, a safety monitoring board comprised of members of the University Hospitals Faculty will evaluate data and adverse events to ensure that there are not ongoing safety concerns that might call for early termination of the study.

Variables/Time Points of Interest

The following data will be recorded as described in the Study Procedures:

- Patient name, medical record number
- Past Medical History
- Past Surgical history
- Medications (including steroids, anticoagulation, opioid use)
- Pre-operative Diagnosis
- Patient Demographics (age, gender, BMI, ASA score)
- Procedure performed
- Time of surgery
- Wound classification
- Estimated blood loss
- Intraoperative transfusion

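### Postoperative opioid use is not clearly among the data to be collected, so a difference between the open-label arms might not show in the planned dataset

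*Combined protocol and SAP*

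**What the plan says.** Data to be collected names opioids once: "Preoperative Medications (including steroids, anticoagulation, opioid use". The Statistical Plan repeats the list under Variables/Time Points of Interest, where the item reads "Medications (including steroids, anticoagulation, opioid use", with no time window. That list says its data are recorded as set out in the study procedures. Neither list has an item for opioid or analgesic use after surgery, after ileus is diagnosed or after randomisation. The study calendar has no row for concomitant medication.

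Postoperative analgesia is described only in outline. Of the recovery pathway, the protocol says: "This includes patient-controlled analgesia pump, oral analgesia and diet on the first postoperative day". Study Overview adds that all patients follow the pathway "along with opioid minimizing measures as is our standard postoperative protocol". After ileus is diagnosed, Study Methods says: "Patients will continue on standard ERAS pathways with the exception of reduction of diet". The same section states: "The patient and surgical team will be able to know which arm of the study the patient is in". One of the four listed discharge criteria is "Adequate oral analgesia". Length of stay, the primary outcome, is counted from surgery to discharge.

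**The concern.** The background describes Entereg as a peripheral opioid antagonist and lists opioid analgesia among the commonly cited contributors to ileus. Opioid exposure is therefore the co-treatment closest to the drug's mechanism. Staff and patients can know the arm, and prescribers might handle analgesia differently because of it. If the trial reports a shorter stay with Entereg, readers will ask whether analgesic care was similar in the two arms. The planned dataset might not be able to answer.

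What is at stake is how a result is explained. The validity of the randomised comparison is not in question.

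**Working it through.** The plan contains no figure on opioid use. Its only computed figure, the sample size, has no bearing here. The check is mainly a reading of the two lists, followed by what the proposed table could show.

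1. **First list.** In Data to be collected, the opioid item is explicitly preoperative. The same list does include postoperative drug items: anti-emetics given and number of Entereg doses. Recording co-treatment is thus within the plan's scope, but opioids after surgery are not listed.

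2. **Second list.** In Variables/Time Points of Interest, the item is undated. It sits between past surgical history and pre-operative diagnosis, and the list refers back to the study procedures, where the matching item is preoperative. The likely meaning is preoperative. On the loosest reading some postoperative opioid use might be recorded, but with no dose, route, timing or post-randomisation window. Hence *not clearly* collected, and *might* not show.

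3. **Other co-treatments.** Postoperative IV fluids are unlisted. So are unscheduled prokinetics, although the restriction covers only scheduled dosing: "no prokinetic or promotility agents will be given as scheduled dosages". Anti-emetics appear in the first list and not in the second. Opioids come first because of the drug's mechanism.

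4. **Precision of the proposed table.** These figures say what the added table could detect. They do not measure harm from its absence. The input is 71 per arm, from Power/Sample Size. The 36 per arm (about half of 71 still in hospital on a given day) is an assumption.
   - Difference in mean daily dose, 95% CI half-width in SD units: t × sqrt(2/n). At 71 per arm: 1.977 × sqrt(2/71) = 0.33 SD. At 36 per arm: 1.994 × sqrt(2/36) = 0.47 SD.
   - Difference in the proportion still on the pump, worst case 50%: 1.96 × sqrt(2 × 0.5 × 0.5/n). At 71 per arm: 0.164, or about ±16 points. At 36 per arm: 1.96 × sqrt(0.5/36) = 0.231, or about ±23 points.
   - The table could show a moderate or large difference. It could not exclude a small one, and it weakens as patients go home.

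5. **Adjustment for a baseline time.** Length of stay = (surgery to ileus) + (ileus to discharge). Patients are randomised when ileus is diagnosed, so the first part is already fixed and treatment cannot change it. Its variation between patients adds noise to the comparison. Adjusting for it multiplies the standard error of the treatment difference by about sqrt(1 − R²), where R² is the share of within-arm variance in stay that it explains. The documents give no R², so no numerical gain is claimed.

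**The case against.** The strongest reply is that nothing in the estimate or test depends on this field. Randomisation protects the comparison, and a difference in opioid use arising after randomisation may be part of the effect of adding Entereg to standard care. Both arms share one recovery pathway with opioid-sparing measures. The exclusion criteria already remove patients with more than 7 days of therapeutic opioids before surgery. The data sit in the medical chart and could be abstracted later. Other co-treatments are missing too.

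Most of this stands, and it sets the severity. It does not close the gap. A shared policy narrows the room for a difference without recording whether one occurred, the exclusion concerns preoperative use, and extraction planned in advance is more credible than extraction after results are known.

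The remedy also has a limit. Daily inpatient dose can be compared only among patients not yet discharged, and discharge defines the primary outcome. If Entereg shortens stay, later days compare differently selected patients. Reporting the number in hospital shows this but does not remove it.

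A reader might also infer more than the documents support:
- *That opioid dosing is left open.* The protocol only summarises the pathway guidelines. It does not reproduce them, and they may fix doses.
- *That analgesia directly drives length of stay.* Oral analgesia is one of four listed discharge criteria, alongside passage of stool and tolerating solid food, in patients who all have ileus. Nothing shows that it is the limiting one.

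**Conclusion.** The gap is real, and its severity is low. Postoperative opioid use is not clearly in the planned dataset, so a difference between the open-label arms after randomisation might go unseen. This rests on reading the undated item as preoperative, which is the likelier reading but not the only one.

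A reader might conclude that the length-of-stay result would be biased or invalid. The documents do not support that: they give no evidence that opioid use will differ between arms, or by how much stay would change if it did. Nor should the significance threshold be taken as the size of the problem. With SD 5.98 and 71 per arm, 1.977 × 5.98 × sqrt(2/71) = 1.98 days is the smallest observed difference reaching p < 0.05. It would be the same for any unlisted variable. What is lost is the ability to describe analgesic care by arm, unless charts are re-abstracted.

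**What to change.** Add to both data lists, from the medication record:

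1. Mean daily opioid dose in morphine equivalents from surgery to randomisation, reported by arm as a baseline characteristic. A daily mean is needed because a total grows with the days elapsed before ileus.
2. Daily opioid dose and route for the first 5 days after randomisation (the maximum Entereg course), with the date and time the pump stopped. Report these descriptively by arm and day, with 95% confidence intervals and the number still in hospital. State that later days compare only patients not yet discharged.

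Do not adjust the primary analysis for item 2, which treatment may affect.

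Prespecify adjustment of length of stay for time from surgery to ileus, which is already on both lists, with item 1 as an optional further covariate. Statistical Methods names no regression model, so one would have to be written in.

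The cost is modest chart-abstraction time for 142 patients, a few REDCap fields and one table. The adjustment for time to ileus costs almost nothing. No new procedures, patients or change in sample size are needed.

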- Intraoperative IV fluids given
- Conversion from laparoscopic to open procedure
- Stoma creation
- Time/day surgery to ileus
- Time from surgery to medication given
- Time from ileus diagnosis to medication given
- Was there return of bowel function (flatus or stool, solid or liquid, stoma output) prior to ileus
- Intra-abdominal infection/anastomotic leak
- Time/day of return of bowel function post ileus (flatus and stool- solid or liquid, and stoma function)
- Time/day of ability to tolerate oral diet (liquid and solid food)
- Nasogastric tube placement and daily output
- Duration of nasogastric tube
- Total number of Entereg doses given
- Post operative complications including reoperation
- Length of stay in hospital, defined as time from surgery to discharge
- 30-day readmissions

Statistical Methods

The study co-investigators and research team will perform statistical analysis. Routine statistical analyses will be utilized for parametric and non-parametric datasets, as appropriate. Demographic data will be analyzed using students t-test or Fishers exact test as appropriate. Categorical data will be analyzed using χ^2 analysis or Fishers exact test where applicable. Normally distributed data will be presented as means \pm SD of the mean, non-normally distributed data will be presented as medians \pm quartiles and categorical data will be presented as raw data and frequencies. A p value of < 0.05 will be considered statistically significant.

Power/Sample Size:

In our practice, patients undergoing open or laparoscopic colectomy without stoma creation who develop POI have a mean length of stay of 10.67 +/- 5.98 days compared to 4.86 days for patients who do not develop POI.

Using this information, to detect a significant decrease in length of stay by 3 days, with a 0.05 level of significance and a power of 80%, a total of 142 patients (71 patients per arm) are required.

Drug supplies (Entereg) for this study will be provided by Merck.

In the event that Merck is unable to provide drug supplies, the University Hospitals Case Medical Center Pharmacy will provide Entereg for this study.

The University Hospitals Case Medical Center Pharmacy will be responsible for distribution of drug in the treatment arm.

All adverse events will be reported per local IRB policy.

Reportable Problem: Any event which meets all three of the following criteria:

- Unexpected (in relation to the protocol and informed consent document),

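### Age and ASA score are collected but used only in significance tests of demographics; prespecified adjustment of the length-of-stay comparison would be a cheap, modest gain

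*Combined protocol and SAP*

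**What the plan says.** The primary outcome is set in Study Overview: "Primary outcome will be hospital length of stay". The lists under Data to be collected and Variables/Time Points of Interest define it: "Length of stay in hospital, defined as time from surgery to discharge". Both lists also include "Patient Demographics (age, gender, BMI, ASA score".

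Statistical Methods gives demographic variables one named use: "Demographic data will be analyzed using students t-test or Fishers exact test as appropriate". For everything else the general statement is that "Routine statistical analyses will be utilized for parametric and non-parametric datasets, as appropriate". The section goes on to cover categorical data, how summaries are presented and the 0.05 threshold. The document names no regression, analysis of covariance, stratified test or covariate list for length of stay.

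Power/Sample Size takes a mean stay of 10.67 days with SD 5.98 in patients who develop ileus. It targets a 3-day reduction at the 0.05 level with 80% power and arrives at 71 per arm, 142 in total.

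**The concern.** The demographic tests are most naturally read as comparisons of the two arms. Read that way, they answer a question that randomisation has already settled: any difference in age or ASA between arms arose by chance. A small p-value there is not evidence of a fault, and a large one does not show that the variable is harmless to the outcome comparison.

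Two things are at stake. The first is precision: if age or ASA predicts length of stay, an unadjusted comparison leaves that variation in the error term and the confidence interval is wider than it need be. The second is prespecification. Baseline p-values invite a decision, after the data are seen, on whether to adjust and for what. Statistical Methods assigns the analysis to the co-investigators and research team, and Study Methods says the surgical team can learn the arm from the medical record. A covariate list fixed in advance is worth more in that setting.

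**Working it through.** **Inputs from the documents** (Power/Sample Size): SD 5.98 days, difference 3 days, 71 per arm, alpha 0.05, target power 80%. Sidedness is not stated; two-sided is assumed.

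**Input not in the documents:** R², the share of length-of-stay variance explained by age and ASA together. Values of 0, 5, 10 and 20% are assumed to show a range.

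**Step 1. The plan's own sample size.** n per arm = 2 × (5.98 × (1.960 + 0.842) / 3)² = 62.4, so 63 per arm; the t-test version gives 63.3, so 64. The plan's 71 is larger than its stated inputs require. A 10% dropout allowance would bring it close (63/0.9 = 70; 64/0.9 = 71.1, rounded up to 72), but none is stated. For the present point, what matters is that 71 is more than enough for the unadjusted test.

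**Step 2. The unadjusted comparison at 71 per arm.**
- SE = 5.98 × √(2/71) = 1.004 days.
- 95% CI half-width = 1.977 × 1.004 = 1.98 days (140 degrees of freedom).
- Noncentrality = 3 / 1.004 = 2.99; noncentral-t power = 84.3%. (The normal approximation gives 84.8%.)

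**Step 3. The adjusted comparison, before any cost.** Residual SD = 5.98 × √(1 − R²). Power is 86.1, 87.9 and 91.3% at R² = 5, 10 and 20%. These figures flatter adjustment, because they charge nothing for estimating the covariate effects.

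**Step 4. The adjusted comparison with the cost of two terms.** With N = 142 and k covariate terms, chance imbalance inflates the variance of the treatment estimate on average by (N − 3)/(N − k − 3). For k = 2 this is 139/137 = 1.0146. So SE = 5.98 × √(1 − R²) × √(2/71) × √1.0146, with 138 degrees of freedom (critical value 1.977).

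| R² (assumed) | SE, days | 95% CI half-width, days | Power |
|---|---|---|---|
| Unadjusted | 1.004 | 1.98 | 84.3% |
| 0 | 1.011 | 2.00 | 83.8% |
| 5% | 0.985 | 1.95 | 85.6% |
| 10% | 0.959 | 1.90 | 87.4% |
| 20% | 0.904 | 1.79 | 90.9% |

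**Step 5. Break-even.** Adjustment pays once (1 − R²) × 1.0146 < 1, that is, R² above 1 − 137/139 = 1.4%. The worst case, R² = 0, costs 84.3 − 83.8 = 0.5 points of power.

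**Step 6. Sensitivity to model size.** At R² = 5%, four terms (for example, ASA entered as categories) give 85.1% and a half-width of 1.96 days. Eight terms give 84.0% and 1.99 days, which is no gain. The list therefore has to stay short.

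**The case against.** The strongest case against the point is that the unadjusted comparison is sound and already exceeds the plan's power target, so adjustment is an optional refinement. Nothing in the documents shows that age or ASA predicts length of stay among patients who already have ileus, and those are the only patients randomised. The gain could be nil, and with several terms the cost is real. Nor does the plan name the length-of-stay test; it leaves parametric or non-parametric methods open, and length of stay may be skewed. Other covariates are better supported: the stratification factors in Randomization, and "Time/day surgery to ileus". The latter is part of the outcome by definition, since stay is counted from surgery while "they will be randomized at the time of diagnosis of postoperative ileus".

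Most of this stands, and it limits the point to low severity. It does not remove it. Two single terms cost at most about half a point of power. Skewness is met by robust standard errors, which keep the target as the difference in means on which the sample size was built. Better covariates elsewhere are a reason to add them, not to leave the demographic tests in place.

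A reader might infer more than the documents support:

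- *That a chance imbalance in age or ASA is a second, separate harm.* It is not. The unadjusted standard error already contains that variation. A covariate correlated 0.3 with length of stay is simply R² = 0.3² = 9%, the same precision loss counted once. It is not bias.
- *That adjustment is free.* Steps 4 to 6 show a small cost that grows with the number of terms.
- *That operating surgeon should be a model term because restarting diet is left to the surgeon.* Surgeon is not among the listed data fields, and the number of surgeons, and so the cost in degrees of freedom, is unknown.

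**Conclusion.** The point holds as a modest loss of efficiency and of prespecification. Age and ASA score are held for analysis, their only stated use is a test that does not help a randomised comparison, and no adjustment of the primary outcome is planned. The primary comparison is neither invalid, biased nor underpowered on the plan's inputs.

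The size depends on an R² that the documents do not give. Over an assumed range of 0 to 20%, the change in power runs from −0.5 to +6.6 points (90.9 − 84.3), and the change in CI half-width from about +0.02 to −0.19 days. These figures also assume a two-sided test, 71 analysed per arm and a linear model with a common residual SD. They take the SD of 5.98 as applying to all enrolled patients, although the plan reports it for colectomy without a stoma and the eligible operations are wider. Severity is low.

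**What to change.** In Statistical Methods, before any outcome data are examined, add wording to this effect: *The between-arm difference in mean length of stay will be estimated by linear regression with terms for treatment arm, age (continuous) and ASA score (single term), plus any design terms used, with robust standard errors. The unadjusted difference will be reported as a supporting analysis.* Keep the total number of terms small, for the reason shown in step 6.

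Replace the significance tests of demographic data with a descriptive table by arm: means and SDs, or medians and quartiles, and counts with percentages.

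The cost is a few sentences. There are no new data fields, no extra patients and no change in care. The statistical downside is about 0.5 points of power if age and ASA turn out to explain nothing.
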